5.5.2 Vital signs

Summary tables will be created to present the descriptive statistics (n, mean, standard deviation, median, minimum, maximum) for vital signs values (temperature, pulse, systolic and diastolic blood pressure) in experimental and control group at baseline and each treatment point.

5.5.3 Physical examination

Physical examination of clinical significance will be listed at baseline and each treatment point.

5.5.4 Laboratory tests

Abnormal values or values of clinical significance according to researchers will be listed at baseline and changes of these values from each treatment point to baseline will be listed in table.

5.5.5 12-Lead Electrocardiograms (ECG)

Abnormal values or values of clinical significance according to researchers will be listed at baseline and changes of these values from each treatment point to baseline will be listed in table.

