#### **Exclusion criteria**

1. Diagnoses of other mental disorders (such as organic mental disorders, schizophrenia, bipolar and related disorders, anxiety disorders, obsessive-compulsive disorders and so on) are made according to DSM-V criteria;
2. Depressive episodes, such as depression caused by hypothyroidism, secondary to a systemic disease or an organic mental disorder caused by a neurological disease;

3. Subjects with a history of attempted suicide, or currently at high suicide risk, or with suicide behavior/attempt, or scoring more than or equal to 3 points on the 10th clause of MADRS scale;
4. Subject whose score of MADRS scale in baseline period will be 25% lower than that in screening period;
5. Subjects with a history of severe or poorly controlled cardiovascular, liver, kidney, blood, endocrine, respiratory diseases, etc;
6. Subjects with a history of epileptic seizures, except for a single febrile convulsion in children;
7. Researchers believe that the results of subjects' physical and laboratory examinations are clinically significant abnormalities in screening or baseline period. The following indicators exceed the following criteria: 1)ALT or AST levels are 1.5 times higher than the upper limit of laboratory normal values. 2)Thyroid Function are 1.1 times higher than the upper or lower limit of normal values. 3) Serum creatinine values are 1.1 times higher than the upper limit of normal values. 4)The levels of blood urea nitrogen are higher than the upper limit of normal values;
8. The result of electrocardiogram (ECG) is abnormal in screening or baseline period, such as male subjects with QTc interval ( $> 450$  ms) and female subjects with QTc interval ( $> 470$  ms) , and the researchers thought it is not suitable for selection;
9. Subjects could not swallow oral medicines or have a history of gastrointestinal surgery or any other diseases that may interfere with drug absorption, distribution, metabolism or excretion;
10. Monoamine oxidase inhibitors (MAOIs) are taken by subjects now or within 2 weeks before screening. Subjects who took antipsychotics, antidepressants or mood stabilizers before randomization and these drugs' cleaning phase had less than five half-lives. Subjects who took fluoxetine within 1 month before screening. Subjects who continue to take Chinese medicines with antidepressant effects specified in the instructions after signing informed consent.

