### **Research visit**

Participants must read and sign the informed consents that are approved by the Ethics Committee(EC) before starting the study. Checks and research procedures are carried out according to the research flow chat.

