### **Treatment Period (Day 14) - Visit 7**

Visit will be conducted on day14 after randomization.

Contents of visit:

1. Scale score: MADRS、 QIDS-SR、 HAMA、 YMRS;
2. Laboratory tests:
  - blood concentration of ethambutamine.
  - complete blood count: hemoglobin (HGB), red blood cell count (RBC), white blood cell count (WBC), neutrophil count (NEUT), lymphocyte count (LY), platelet count (PLT);
  - routine urine: PH, white blood cells, erythrocyte (ERY), nitrite (NIT), protein, glucose (GLU), ketone body (KET), urinary cholanogen (UBG), bilirubin;
  - blood biochemical examination: aspartate aminotransferase (AST), glutamate aminotransferase, alkaline phosphatase (ALP), glutamyl transpeptidase (GGT), lactate dehydrogenase (LD), total protein, albumin (ALB), urea nitrogen (BUN), creatinine, creatine kinase (CK), total bilirubin (TBIL), direct bilirubin (DBIL), uric acid, blood sugar (Glu), triglyceride (TG), total cholesterol (TC), high density lipoprotein (HDL) ,low density lipoprotein (LDL), sodium (Na), potassium (K), chlorine, phosphorus (P), calcium (Ca), prolactin (PRL);
3. ECG: 12 leads cardiogram;

4. Vital signs: including blood pressure (sitting position), heart rate, respiratory rate, body temperature and weight;
5. Records of adverse events;
6. Records of combined medication;
7. Drugs recovery and dispensing;

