5.5 Safety Analysis

5.5.1 Adverse events

Adverse events occurred in experimental and control group will be summarized according to following contents.

1. Any treatment emergent adverse events
2. Related treatment emergent adverse events

3. Serious treatment emergent adverse events
4. Adverse Events Leading to Treatment Discontinuation
5. Adverse Events Leading to Death
6. Any treatment emergent adverse events by severity
7. Related treatment emergent adverse events by severity

These events will be displayed in data lists.

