5.5.6 Systematic Assessment for Treatment Emergent Events (SAFTEE)

In the study, summary tables will be created to present treatment emergent events of subjects at baseline and each treatment point.

6. Instructions

This statistical analysis plan(SAP) is to develop from the research protocol (Protocol

version Number: 3.0). The contents of SAP may be modified with the deepening of the study.

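### Read literally, SAP 5.5.4 and 5.5.5 leave out of both outputs any laboratory or ECG abnormality that first appears at Day 14 or Day 42

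*SAP*

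**What the plan says.** SAP 5.5.4 and 5.5.5 use the same sentence: "Abnormal values or values of clinical significance according to researchers will be listed at baseline and changes of these values from each treatment point". It ends by saying that these changes, taken against baseline, go into a table. Neither section mentions treatment group.

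Other text that bears on the point:

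- **SAP 5.5.2 (vital signs)** promises descriptive statistics "in experimental and control group at baseline and each treatment point".
- **SAP 5.5.1 (adverse events)** states that "Adverse events occurred in experimental and control group will be summarized according to following contents". The categories include treatment-emergent, related and serious events, and events by severity.
- **SAP 5.5.6 (SAFTEE)** states that "summary tables will be created to present treatment emergent events of subjects at baseline and each treatment point". It does not mention group.
- **SAP 5.3.2** has rows for abnormal laboratory and ECG results, but only in the baseline table.
- **Protocol, Visit 7 (Day 14) and Visit 10 (Day 42±1)** each list blood count, urine, biochemistry and "ECG: 12 leads cardiogram".
- **Protocol, Exclusion criteria 7 and 8.** Criterion 7 covers patients for whom the researchers believe that the results of physical and "laboratory examinations are clinically significant abnormalities in screening or baseline period". Criterion 8 covers an abnormal ECG, "and the researchers thought it is not suitable for selection".
- **Protocol, Research visit** states that "Checks and research procedures are carried out according to the research flow chat". That chart is not shown in the text available for review.

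**The concern.** Safety is one of the two aims in SAP section 1. For laboratory and ECG safety data, the result of most interest is usually a change from normal to abnormal on treatment, compared between arms. The sentence in 5.5.4 and 5.5.5 first selects values by their status at baseline and then follows only those. An analyst who programmed it as written would report how pre-existing abnormalities evolved and would have no instruction to report new ones.

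Day 14 is the end of the ethosuximide or placebo phase, so it is the visit where an effect of the study drug on these measures would be looked for. If the two sections do not cover new abnormalities, by-group reporting of them depends on a separate decision to record each one as an adverse event.

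**Working it through.** The SAP states no figure here that could be reproduced. The check is a reading of the rule against the possible outcomes, followed by a count of what the two sections govern.

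**Step 1. Apply the sentence to each combination of states.** Its second half refers to these values, and the nearest antecedent is the values listed at baseline.

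| At baseline | At Day 14 or 42 | Baseline list | Change table |
|---|---|---|---|
| Abnormal | Abnormal | Yes | Yes |
| Abnormal | Normal | Yes | Yes |
| Normal | Normal | No | No |
| Normal | Abnormal | No | No |

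The last row is the treatment-emergent case, and on this reading it is in neither output.

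**Step 2. Look for another output that would capture it.**

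- SAP 5.3.2 covers baseline only.
- SAP 3.2 names laboratory tests and ECG as safety measures but specifies no output.
- SAP 5.5.1 would capture it by group if it were recorded as an adverse event. Adverse events are recorded at Visits 7 and 10, but neither document says when an abnormal laboratory or ECG value becomes one.
- SAP 5.5.6 might capture it if SAFTEE elicited it, but that section does not say that its tables are by group. The visit lists do not name SAFTEE; the flow chart may.

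No route is therefore assured, and only 5.5.1 is by group.

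**Step 3. Count what the two sections govern** (Protocol, Visits 7 and 10; SAP 2.2).

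- Laboratory parameters per visit: 6 blood count + 9 urine + 24 biochemistry = 39. The drug concentration assay is not counted.
- Laboratory panels after baseline: 40 patients × 2 visits = 80, or 20 × 2 = 40 per arm.
- ECGs after baseline: 40 × 2 = 80, or 40 per arm.

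These are scheduled assessments if all patients complete, not affected results. The documents give no rate of new abnormalities, so none is assumed.

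**Step 4. Check what baseline means for these data.** The protocol sets the baseline period as day 1, but the Visit 1 list has no laboratory test or ECG. The only pre-dose ones in the visit lists are at Visit 0. However, exclusion criteria 7 and 8 speak of results at screening or baseline, and the flow chart is not shown, so Day 1 tests cannot be ruled out. Change from baseline needs a definition on any reading of the sentence.

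**The case against.** The strongest reply is that this is a strict reading of loose English. The same sentence describes changes running from treatment point to baseline, the reverse of usual usage, so its grammar is a weak guide to intent. The phrase about these values could mean the laboratory or ECG parameters in general. On the strict reading, the first half also largely repeats the baseline rows in SAP 5.3.2, which would be odd in a safety analysis section. This stands: a wider intent is plausible. But no SAP text states it, and two analysts could produce different tables from the sentence.

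The contrast with 5.5.2 and 5.5.3, which do name each treatment point, does not settle the matter. SAP 5.5.3 uses that phrase for physical examination, which the visit lists name only at Visits 0 and 1, so it may be standard wording. Nor is the silence about group peculiar to these sections, since 5.5.3 and 5.5.6 are also silent.

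The adverse event route is real. A new abnormality that the researcher judges to be an adverse event would be summarised by group under 5.5.1. That narrows the gap but does not close it.

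A reader might also infer from exclusion criteria 7 and 8 that almost nothing would be followed. The documents do not show this. The numeric limits in criterion 7 cover only ALT or AST, thyroid function, creatinine and urea nitrogen. Minor abnormalities in lipids, prolactin, blood count or urine can enter the trial and would be followed, and no rate is given.

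**Conclusion.** The point holds as a matter of wording. Followed literally, 5.5.4 and 5.5.5 do not report a laboratory or ECG abnormality that first appears at Day 14 or Day 42, and no other output is certain to. The sections govern 39 parameters at two visits (80 panels) and 80 ECGs if follow-up is complete. The number of results affected is unknown.

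This rests on two assumptions: that the sentence is applied as written, and that no unseen part of the flow chart changes how these abnormalities are recorded.

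A reader might infer that new abnormalities would go unreported altogether, or that the sponsor chose to restrict reporting. Neither is supported: the adverse event summaries could carry them, and the wording is too loose to show intent. The data are collected either way and the efficacy analysis is unaffected. This is a weakness in a descriptive safety output that should be corrected, not a flaw in the trial's design.

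**What to change.** In both 5.5.4 and 5.5.5, replace the sentence with:

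*All abnormal or clinically significant values will be listed by group at baseline and each treatment point, whatever the baseline status, with the change from baseline.*

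Add that baseline for laboratory tests and ECG is the last value before the first dose. This works whether that value comes from Visit 0, the only pre-dose source in the visit lists, or from a Day 1 test that the flow chart may schedule.

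Optional: a descriptive shift table by arm (normal or abnormal at baseline, against normal or abnormal at Day 14 and at Day 42), without p-values.

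The cost is one sentence in each of two sections, one definition and a slightly longer listing. It needs no new assessments, and SAP section 6 already allows the plan to be modified.

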5.5.6 Systematic Assessment for Treatment Emergent Events (SAFTEE)

In the study, summary tables will be created to present treatment emergent events of subjects at baseline and each treatment point.

6. Instructions

This statistical analysis plan(SAP) is to develop from the research protocol (Protocol

version Number: 3.0). The contents of SAP may be modified with the deepening of the study.
